8.2 Time Period and Frequency for Event Assessment and Follow-Up

Unanticipated problems will be recorded throughout the study.

Reportable events will be recorded starting at the time of the start of the study procedure through subject discharge from the NICU. At each study visit, the investigator will inquire about the occurrence of AE/SAEs since the last visit. Events will be followed for outcome information until resolution or stabilization.

8.3 Characteristics of an Adverse Event

8.3.1 Relationship to Study Intervention

To assess relationship of an event to study intervention, the following guidelines are used:

1. Related (Possible, Probable, Definite)
 - a. The event is known to occur with the study intervention.
 - b. There is a temporal relationship between the intervention and event onset.
 - c. The event abates when the intervention is discontinued.
 - d. The event reappears upon a re-challenge with the intervention.
2. Not Related (Unlikely, Not Related)
 - a. There is no temporal relationship between the intervention and event onset.
 - b. An alternate etiology has been established.

8.3.2 *Expectedness of SAEs*

The Study PI will be responsible for determining whether an SAE is expected or unexpected. An adverse event will be considered unexpected if the nature, severity, or frequency of the event is not consistent with the risk information previously described for the intervention.

8.3.3 *Severity of Event*

We will assign toxicity grades to indicate the severity of adverse experiences and toxicities. For maternal adverse events, toxicity grading consistent with NCI-CTCAE v 5.0 will be used for this protocol. The purpose of using the NCI-CTCAE system is to provide standard language to describe toxicities and to facilitate tabulation and analysis of the data and assessment of the clinical significance of treatment-related toxicities.

Any adverse events not included in the NCI-CTCAE listing will be recorded and graded 1 to 5 according to the General Grade Definition provided below:

Grade 1	Mild	Transient or mild discomforts (< 48 hours), no or minimal medical intervention/therapy required, hospitalization not necessary (non-prescription or single-use prescription therapy may be employed to relieve symptoms, e.g., aspirin for simple headache, acetaminophen for post-surgical pain).
Grade 2	Moderate	Mild to moderate limitation in activity, some assistance may be needed; no or minimal intervention/therapy required, hospitalization possible.
Grade 3	Severe	Marked limitation in activity, some assistance usually required; medical intervention/therapy required, hospitalization possible.
Grade 4	Life-threatening	Extreme limitation in activity, significant assistance required; significant medical/therapy intervention required, hospitalization, or hospice care probable.
Grade 5	Death	Death

For additional information and a printable version of the NCI-CTCAE v. 5.0 manual, consult the NCI-CTCAE website,
https://ctep.cancer.gov/protocolDevelopment/electronic_applications/ctc.htm#ctc_50.

The NCI-CTCAE system has not been validated for neonatal subjects. Therefore, neonatal adverse events will be graded according to the International Neonatal Consortium (INC) Neonatal Adverse Event Severity Scale [24].

Grade 1	Mild	Mild; asymptomatic or mild symptoms; clinical or diagnostic observations only; no change in baseline age-appropriate behavior; no change in baseline care or monitoring indicated
Grade 2	Moderate	Moderate; resulting in minor changes of baseline age-appropriate behavior; requiring minor changes in baseline care or monitoring
Grade 3	Severe	Severe; resulting in major changes of baseline age-appropriate behavior or non-life threatening changes in basal physiological processes; requiring major change in baseline care or monitoring
Grade 4	Life-threatening	Life-threatening; Resulting in life-threatening changes in basal physiological processes; requiring urgent major change in baseline care
Grade 5	Death	Death related to AE

More information regarding this scale can be found here: <https://www.ncbi.nlm.nih.gov/pmc/articles/PMC6943241/#SP6>

8.4 Reporting Procedures

All AEs, except as defined above, will be followed until the time the event is resolved or medically stable, or until subject is discharged from hospital, whichever comes first. AEs may be discovered through any of these methods:

- Observing the subject
- Questioning the subject, which will be done in an objective manner
- Receiving an unsolicited complaint from the subject
- Review of medical records/source documents

All AEs must be recorded accurately on the Adverse Event log for each study subject. The date of onset and duration of the AE, grade, whether it was expected or unexpected, action taken, date of resolution (if applicable) and outcome of the event must be recorded. The investigator will treat subjects experiencing adverse events appropriately and observe them at suitable intervals until their symptoms resolve or their status stabilizes or they are discharged from the hospital.

SAEs and unanticipated problems will be reported promptly to the IRB(s) according to local regulations and guidelines.

The PI and delegates are responsible for notifying the DSMB chair of all SAEs. The DSMB will evaluate the relationship of the SAE to the underlying disease. The PI, in cooperation with the DSMB, will determine whether the SAE is unexpected in nature and make a recommendation for any further action. The primary consideration is the study subjects' safety. All other AEs will be reported to the DSMB for review and adjudication at regular intervals.

8.4.1 Reporting of SAEs and AEs to the FDA

The Sponsor-Investigator (SI) will report unanticipated adverse device effects to the FDA and other applicable health authorities within the required timelines, as specified in 21 CFR 812.150, within 10 working days of the SI becoming aware of the event. As defined in 21 CFR 812.3(s) an unanticipated adverse device effect means any serious adverse effect on health or safety or any life-threatening problem or death caused by, or associated with, a device, if that effect, problem, or death was not previously identified in nature, severity, or degree of incidence in the investigational plan or application (including a supplementary plan or application), or any other unanticipated serious problem associated with a device that relates to the rights, safety, or welfare of subjects.

8.5 Halting Rules

The study will be stopped if there is one maternal death occurring within 48 hours of the embolization procedure that is determined by the DSMB to be plausibly related to the study procedure.

More information regarding study stopping rules can be found in the Statistical Considerations section.

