3.2 Study Outcome Measures

Primary (safety) endpoint: The procedure is deemed safe if

- 1) **None** of the following unacceptable events occur within 7 days of fetal embolization:
 - a) Fetal death
 - b) Fetal intracranial hemorrhage, either parenchymal or extra-axial, other than petechial hemorrhage. A petechial hemorrhage is seen as focal staining of the brain parenchyma by blood products on MRI, is not associated with mass effect, and there are minimal neurologic sequelae. Petechial hemorrhages are usually considered non-serious adverse events in trials.
 - c) Maternal death
- 2) **None** of the following unacceptable events occur between fetal embolization and delivery:
 - a) Intra-procedural and post-procedural morbidity to the fetus and mother, probably related to the fetal intervention, e.g. placental abruption with subsequent sequelae
 - b) Preterm delivery < 28 weeks, probably related to the fetal intervention
 - c) Maternal blood transfusion or unanticipated surgical intervention, probably related to the fetal intervention
 - d) Presence of fetal imaging evidence of new brain injury in a location or pattern unexpected for the natural history of vein of Galen malformation, probably related to the fetal intervention

Secondary (efficacy) endpoint: The procedure is deemed efficacious if **none** of the following serious postnatal events occur within 30 days of birth:

1. Urgent neonatal embolization is needed. Without fetal intervention, we'd expect 80% of the cohort to require such intervention.
2. Neonatal death. Without fetal intervention, we'd expect a mortality rate of 40% in this cohort.
3. Brain MRI within the first three weeks after birth reveals parenchymal brain injury (acute infarct or gliosis) affecting > 10% of the supratentorial brain volume. Without fetal intervention, we'd expect 30% of patients in this cohort to show this kind of injury.

Additional efficacy data to be collected includes assessment of the neurocognitive development in the treated cohort. Subjects will be followed and assessed until age 24 months and results will be compared to historical controls of NAR VOGM patients treated using the current neonatal paradigm.

Comparison of outcomes will be made with published (meta-analysis and UK national data [1, 2, 6, 7]) and institutional historical results for fetuses who receive standard neonatal or post-neonatal treatment.

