11.3 Safety Review

Two-stage design for safety endpoint

In Stage 1, up to 11 evaluable patients will be enrolled (**Table 2**). Out of 11 patients, if 3 or more patients experience an unacceptable event (see definition in Section 3.2 above and recapitulated below Table 2), the intervention is unsafe and not worthy of further study. If 2 or fewer experience any unacceptable event, the trial will proceed to Stage 2, where an additional 9 evaluable patients will be enrolled, for a total of $N=20$ evaluable patients. Out of $N=20$ patients, if 4 or more patients experience any unacceptable event, the intervention is unsafe and not worthy of further study. If 3 or fewer patients experience any unacceptable event, the intervention is sufficiently safe and worthy of further study. In addition, in case of a single maternal death, the study will be halted pending review by the DSMB and the FDA.

This design tests the null hypothesis that the rate of unacceptable events is $P > 30\%$ versus the alternative that $P < 5\%$. The total type I error rate is 0.097 and the power is 97.5%. If the intervention is truly unsafe, there is a 68.7% probability of early trial termination.

Table 2: Decision rules for safety based on the optimum two-stage design.

	Cumulative number of patients with unacceptable events	Decision
Stage 1: Enroll 11 patients	3 or more	Terminate the trial: agent not worthy of further study
	2 or fewer	Inconclusive result: proceed to Stage 2
Stage 2: Enroll 9 additional patients	4 or more	Terminate the trial: agent not worthy of further study
	3 or fewer	Trial concludes: agent worthy of further study

- 1) Unacceptable events within 7 days of fetal embolization include:
 - a) Fetal death
 - b) Fetal intracranial hemorrhage, either parenchymal or extra-axial, other than petechial hemorrhage. A petechial hemorrhage is seen as focal staining of the brain parenchyma by blood products on MRI, is not associated with mass effect, and there are minimal neurologic sequelae. Petechial hemorrhages are usually considered non-serious adverse events in trials.
 - c) Maternal death
- 2) Unacceptable events occur between fetal embolization and delivery include:
 - a) Intra-procedural and post-procedural morbidity to the fetus and mother, probably related to the fetal intervention, e.g. placental abruption with subsequent sequelae
 - b) Preterm delivery < 28 weeks, probably related to the fetal intervention

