11.5 Timing of safety and efficacy rules

The safety endpoint is observed from Day 0 (the day of fetal intervention) to Day 7 post-intervention. The efficacy endpoint is observed from the birth to Day 30 of life. Both safety and efficacy decision rules must be satisfied before enrollment to Stage 2 is allowed. Prior to initiating accrual at Stage 2, a sensitivity analysis will be performed to determine if both the safety and efficacy rules would be triggered. Hence, trial enrollment for Stage 2 may be suspended after the enrollment of the 11th patient to allow observation up to Day 30 of life of the most recently treated patient.

The safety and efficacy rules are to be interpreted as specifying that the trial will stop as soon as either criterion is reached; e.g., if the first 3 evaluable patients experience unacceptable prenatal events (safety rule), or the first 6 patients experience serious postnatal events (efficacy rule), then the trial stops immediately. Beyond the 11th patient, the trial halts as soon as 4 unacceptable prenatal events or 10 serious postnatal events occur.

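### A procedure-related fetal death from Day 8 to delivery is not named in the primary safety count, and the two maternal-death halting rules are not reconciled

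*Combined protocol and SAP*

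**What the plan says.** **The safety count.** Section 3.2 defines the primary endpoint by two lists, and Section 11.3 repeats them.

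- List 1 requires that none "of the following unacceptable events occur within 7 days of fetal embolization". It holds fetal death, non-petechial intracranial hemorrhage and maternal death, with no relatedness test. Section 11.3 uses the same window: "Unacceptable events within 7 days of fetal embolization include".
- List 2 runs from embolization to delivery and requires probable relatedness. Item 2a is "Intra-procedural and post-procedural morbidity to the fetus and mother, probably related to the fetal intervention, e.g. placental abruption with subsequent sequelae". Items 2b to 2d are preterm delivery before 28 weeks, maternal transfusion or unanticipated surgery, and new fetal brain injury of an unexpected pattern. Death is not in list 2.

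**The observation window.** Section 11.5 states: "The safety endpoint is observed from Day 0 (the day of fetal intervention) to Day 7 post-intervention".

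**The decision rule.** Under 11.3 the trial ends if 3 or more of the first 11 patients have an unacceptable event. The procedure is unsafe if 4 or more of 20 do.

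**Maternal death and halting.** Section 8.5 states: "The study will be stopped if there is one maternal death occurring within 48 hours of the embolization procedure", on condition that the DSMB finds the death plausibly related to the procedure. It then refers the reader to the statistical section for more on stopping rules. There, 11.3 adds that "in case of a single maternal death, the study will be halted pending review by the DSMB and the FDA". Section 11.5, which describes when the trial stops, does not mention maternal death.

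**The concern.** The main concern is the count. Fetal death is the gravest fetal outcome of a first-in-human fetal procedure, yet it is tied to a 7-day window while lesser related harms are counted to delivery. The protocol's own risk list (2.4.1) names procedure-related fetal death and stillbirth. It also names infection, membrane rupture and abruption, whose effects need not be over by Day 7. If a related late fetal death is not counted, the trial can pass its safety rule with that death outside it.

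The efficacy endpoint does not close the gap. It covers events within 30 days of birth, and 11.4 defines a responder as a patient without a serious postnatal event. A fetus that dies in utero has none. Under 5.4.2 a subject who completed the intervention is evaluable, and the plan does not say how such a subject is classified for efficacy.

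The second concern is that the DSMB must judge whether stopping criteria are met (Section 9), while 8.5 and 11.3 state different criteria for maternal death.

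**Working it through.** **1. The plan's own figures.** Inputs from 11.3: n1 = 11, continue if X1 ≤ 2; 9 more patients, declare safe if the total ≤ 3; event rates 30% (null) and 5% (alternative).

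P(declared safe) = Σ over x = 0, 1, 2 of P(X1 = x) × P(X2 ≤ 3 − x), with X1 ~ Bin(11, p) and X2 ~ Bin(9, p).

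- p = 0.30: 0.0198 × 0.7297 + 0.0932 × 0.4628 + 0.1998 × 0.1960 = 0.0144 + 0.0431 + 0.0392 = 0.0967 (stated 0.097).
- p = 0.05: 0.5684 + 0.3266 + 0.0805 = 0.9755 (stated 97.5%).
- Early termination at p = 0.30: P(X1 ≥ 3) = 0.6873 (stated 68.7%).

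All three reproduce. The arithmetic is sound. The issue is which events enter X.

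**2. Cases set against the text** (deaths before delivery)

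| Event | 8.5 | 11.3 halt | Safety count |
|---|---|---|---|
| Related maternal death, 24 hours | stop | halt | counted |
| Related maternal death, Day 5 | not triggered | halt | counted |
| Related maternal death, Day 10 | not triggered | halt | not named; counted only if a list 2 item also applies |
| Related fetal death, Day 5 | not covered | not covered | counted |
| Related fetal death, Day 10 | not covered | not covered | not named; counted only if a list 2 item also applies |

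The last row is the gap: no death-specific halt and no certain count.

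**3. Length of the uncovered period.** Treatment is allowed from 23 weeks (5.1). Assuming term near 40 weeks, 40 − 23 − 1 = 16 weeks at most lie between Day 7 and delivery. Later treatment shortens this.

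**4. Effect at the boundaries.** With 2 counted events among 11, one uncounted late death separates continuing (2 of 11) from terminating (3 of 11). At the end it separates 3 of 20 from 4 of 20.

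**5. Illustration only.** The documents give no late-death rate. Suppose the true rate of patients with any unacceptable outcome is 30%, and m percentage points of that are patients whose only such outcome is an uncounted late death. Then p = 0.30 − m enters the formula above:

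| m (assumed) | P(declared safe) | Stage 1 termination |
|---|---|---|
| 0 | 0.097 | 68.7% |
| 1 point | 0.114 | 66.1% |
| 2 points | 0.133 | 63.4% |
| 3 points | 0.155 | 60.5% |
| 5 points | 0.206 | 54.5% |

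**6. Section 11.5 against list 2.** A safety endpoint observed only to Day 7 cannot register items 2a to 2d, which run to delivery. The two statements contradict each other whatever is decided about death.

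**The case against.** **Late deaths may be caught through list 2.** Item 2a is open-ended and covers post-procedural morbidity to fetus and mother up to delivery. A death judged related would often be attributed to a complication that qualifies under 2a, 2c or 2d, or be followed by a related delivery before 28 weeks under 2b. This stands in part. It means that a reader who infers that every late related death scores zero goes too far. But the lists name death apart from morbidity, and 7.4 treats fetal deaths as a tally of their own. No passage says that 2a includes death. A related fetal death with no separately qualifying event remains outside the count.

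**Maternal death cannot pass unnoticed.** This stands. Section 11.3 halts for any maternal death, so the counting gap matters mainly for fetal death.

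**Section 8.5 and 11.3 can both be obeyed.** A reader might infer that the protocol has three conflicting triggers, or that the site may carry on under 8.5 when 11.3 requires a halt. The documents support neither. Section 3.2 is a counting rule and not a trigger. Section 8.5 does not say that its condition is the only one, it authorises no continuation, and it points to the statistical section, where 11.3 binds in every case. The two rules can be read as a pause for any maternal death and a stop for an early, plausibly related one. What remains is that no passage states this two-tier reading, and that windows, relatedness tests and actions differ.

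**There are backstops.** Every serious adverse event goes to the DSMB (8.4, Section 9), and 5.5 allows termination for unacceptable risk. This is true, but discretion does not settle how the prespecified count treats a late death.

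**Conclusion.** The point holds for the count. Read literally, a procedure-related fetal death between Day 8 and delivery, with no other listed event, is neither an unacceptable safety event nor a serious postnatal event. Section 11.5 makes this worse by ending safety observation at Day 7, against list 2.

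The size is unknown, because it depends on a late-death rate that the documents do not give. The figures in step 5 of the working rest on assumed shares and are not evidence that the error rate is inflated by that much. What is certain is that a single event can reverse the decision at 3 of 11 or 4 of 20. The stated 0.097, 97.5% and 68.7% are correct for whatever events are counted.

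On halting, the finding is limited to two unreconciled passages, 8.5 and 11.3. No view is taken here on which window, relatedness test or action is right.

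**What to change.** 1. In list 2 of 3.2 and of 11.3, add an item for maternal or fetal death judged probably related to the intervention, so that related deaths from Day 8 to delivery are counted.
2. In 11.5, align the safety observation window with list 2, so that it runs to delivery.
3. Reconcile 8.5 and 11.3 on maternal death: state how the two rules relate, or merge them, and cross-refer to the result from 11.5.

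**Cost.** This is protocol wording, with no change to sample size or boundaries. Observing safety to delivery need not lengthen the pause between stages, because 11.5 already provides for suspending Stage 2 enrollment until Day 30 of life of the most recently treated patient. The safety count can only become stricter. If late related deaths came on top of a 5% event rate, the chance of declaring the procedure safe would fall from 0.975 to 0.959 with 1 added point, 0.936 with 2 and 0.840 with 5 (same formula at p = 0.06, 0.07 and 0.10; the added points are assumptions).

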9 STUDY OVERSIGHT

In addition to the PI's responsibility for oversight, study oversight will be under the direction of a Data and Safety Monitoring Board (DSMB) composed of five senior faculty of medical schools not affiliated with the study. Members will have expertise in pediatric neurointerventions, management of vein of Galen malformations, neonatology, maternal-fetal medicine, and fetal/neonatal cardiology. The DSMB will meet as outlined in the DSMB charter.

The DSMB will make recommendations to the PI and the Institutional Review Boards at Boston Children's Hospital and the Brigham and Women's Hospital about protocol changes necessary to protect the scientific validity of the study or to protect study participants, including study termination. The DSMB will meet by phone or video conference at least twice a year after the start of patient enrollment to review all procedures. All serious adverse events will result in notification of the DSMB, which will evaluate the severity of the event, the relationship to the study intervention, and whether stoppage criteria have been met. The DSMB charter indicates additional time points when a DSMB meeting may need to be convened for evaluation of continuation of the study.

10 CLINICAL SITE MONITORING

Clinical site monitoring is conducted to ensure that the rights of human subjects are protected, that the study is implemented in accordance with the protocol and/or other operating procedures, and that the quality and integrity of study data and data collection methods are maintained. Monitoring for this study will be performed by an independent qualified monitor. The monitor will evaluate study processes and documentation based on the International Conference on Harmonisation (ICH), E6: Good Clinical Practice guidelines (GCP).

Details of clinical site monitoring will be documented in the Monitoring Plan. The Monitoring Plan will specify the frequency of monitoring, monitoring procedures, the level of clinical site monitoring activities (e.g., the percentage of subject data to be reviewed), and the distribution of monitoring reports. The monitor will conduct monitoring activities and provide reports of the findings and associated action items in accordance with the details described in the MP. Documentation of monitoring activities and findings will be provided to the site study team and the study PIs.

